6.6 Dose Selection and Modification

Dose escalation will proceed according to the SMC recommendation until the 50 mg dose level or the MTD is reached (whichever is lower). For further dose cohorts, a SMC will meet and review all available data to provide recommendations on the next dose level. In case escalation should proceed to doses higher than 50 mg, a protocol amendment will be submitted. Details are described in the SMC charter. The SMC receives outputs of a Bayesian dose-toxicity model estimated DLT probabilities for potential next dose levels. The Bayesian model will be based on prior, observed number of evaluable participants and number of participants with DLT. Further details on the Bayesian model are provided in Section 9.4.2. Further details on the SMC are provided in Section 10.

A DLT is defined as any of the AEs listed below as assessed by the Investigator and/or the Sponsor at any dose and regimen, and judged not to be related to the underlying disease or any previous or concomitant medication or concurrent condition occurring during the DLT observation period (first treatment cycle), according to the NCI-CTCAE v 5.0. Any DLT must be confirmed by the SMC.

During the DLT assessment period: Treatment with transfusions or growth factors (e.g., G-CSF, erythropoietin) is not permitted. Transfusions are only permitted if clearly related to multiple myeloma.

Participants who develop a DLT will permanently discontinue treatment.

Participants who did not receive $\geq 80\%$ of the planned cumulative dose or missed more than 20% of doses in the DLT period will not be considered in the DLT analysis set unless they experienced a DLT.

AEs judged as DLT will include:

- Any Grade ≥ 3 nonhematologic AE with exception of:
 - Single laboratory values out of abnormal range that have no clinical correlate, and resolve to Grade ≤ 1 or to Baseline within 7 days with adequate medical management
 - Grade 3 diarrhea persisting ≤ 72 hours after initiation of medical management
 - Nausea and vomiting of ≤ 72 h duration with adequate and optimal therapy
 - Transient (< 1 week) Grade 3 fatigue, local reactions, flu-like symptoms, fever, and headache (≤ 72 h) that resolves to Grade ≤ 1 with adequate treatment
 - Grade 3 nonrecurrent skin toxicity that resolves to Grade ≤ 1 in less than 7 days after initiation of medical management
 - Asymptomatic Grade ≥ 3 lipase or amylase elevation not associated with clinical manifestations of pancreatitis.

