- Hy's law: Evidence of hepatocellular toxicity without clear alternative reason to explain the observed liver-related laboratory abnormalities, such as increase in AST or ALT of ≥ 3 x

ULN elevation and elevation of serum total bilirubin $\geq 2 \times$ ULN, without initial findings of cholestasis (elevated serum ALP) or other apparent clinical causality (eg viral hepatitis A, B, C or co-medication)

- Any death not clearly due to the underlying disease or extraneous causes
- Any Grade ≥ 4 hematologic AE, and:
 - Grade ≥ 3 febrile neutropenia with ANC $<1000/\text{mm}^3$ and a single temperature of $>38.3^\circ\text{C}$ (101°F) or a sustained temperature of $\geq 38^\circ\text{C}$ (100.4°F) for more than 1 h
 - Grade ≥ 3 thrombocytopenia with medically concerning bleeding
 - Grade 4 thrombocytopenia lasting >7 days, or platelets $<10,000/\text{mm}^3$ at any time

Except:

- Isolated Grade 4 lymphopenia without clinical correlate
- Any Grade 4 neutropenia of < 7 days duration not associated with any clinical symptoms.

- Neuropathic Pain or Peripheral Sensory or Motor Neuropathy:
 - Any aggravation by 2 grades or any Grade ≥ 3 (severe symptoms: limiting self-care Activity of Daily Life [ADL]).
- Any TEAE the SMC deems clinically relevant, that impairs daily function or abnormality occurring in participants treated with M3258 -/+ combination with dexamethasone at any time in Cycle 1 and any toxicity at any time in Cycle 1
- A study intervention-related TEAE (observed in subsequent cycles) that in the opinion of the SMC is of potential clinical significance such that further dose escalation would expose participants to unacceptable risk.

Any DLT will be confirmed by the SMC.

Table 11 describes the recommended individual dose modifications related to M3258-related neuropathic pain or peripheral sensory or motor neuropathy when experienced by participants outside of DLT period. **Table 12** describes the individual dose modifications and temporary or permanent treatment discontinuations for M3258-related hematologic toxicities when experienced by participants outside of DLT period. **Table 13** describes the individual recommended temporary treatment discontinuations for M3258-related general toxicities when experienced by participants outside of DLT period.

Table 11 Recommended Dose Modification for New Onset or Worsening Neuropathic Pain and/or Peripheral Sensory or Motor Neuropathy (outside of DLT Period)

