Treatment cycles with M3258 -/+ combination with dexamethasone will be repeated every 21 or 28 days; hence, for a cycle of treatment to begin, the participant's blood ANC must be \geq 1,000 mm³ and the platelet count must be \geq 75,000 mm³. Additionally, all other toxicities considered to be related to study intervention must have resolved to \leq Grade 1 or to the participant's Baseline value.

If the participant fails to meet the above-cited criteria for treatment, re-initiation of the next cycle of treatment should be delayed for one week. At the end of which, the participant should be re-evaluated to determine whether the criteria for re-treatment have been met. If a delay in the initiation of the next cycle of more than two weeks is required because of incomplete recovery from toxicity, then this event should be considered a DLT. If toxicity does not resolve by two weeks, then the participant should be discontinued from the study. This decision will be made in the context of emerging clinical data and in consultation with Sponsor Medical Responsible. If, in the opinion of the Investigator and the Sponsor Medical Responsible, it is in the participant's best interest to continue the treatment with M3258 -/+ combination with dexamethasone, the study intervention will only be resumed after recovery from toxicity to \leq Grade 1 or Baseline values. Additionally, the dose of study intervention should be reduced by at least 1 dose levels. If the DLT recurs upon resuming study intervention at a lower dose, the study intervention should immediately be discontinued. For the first study cohort, no dose reduction will be allowed.

7

Discontinuation of Study Intervention and Participant Discontinuation/Withdrawal

7.1

Discontinuation of Study Intervention

Stopping Rules for Individual Participants:

The Investigator must consider discontinuation of study intervention for abnormal liver function when a participant meets one of the conditions outlined in Section 6.6 or if the Investigator believes that it is in best interest of the participant.

All events of ALT \geq 3 \times ULN and bilirubin \geq 2 \times ULN ($> 35\%$ direct bilirubin) or ALT $>$ 3 \times ULN and international normalized ratio (INR) $>$ 1.5, if INR measured, may indicate potential severe liver injury (possible Hy's Law) and must be reported as an AE and SAE.

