If a clinically significant finding in ECG recording is identified (including, but not limited to changes from Baseline in QT interval corrected using Fridericia's formula [QTcF]) after enrollment, the Investigator or qualified designee will determine if the participant can continue in the study and if any change in participant management is needed. This review of the ECG printed at the time of collection must be documented. Any new clinically relevant finding should be reported as an AE.

The SoA (Table 1 and Table 2 for Part A; Table 3 and Table 4 for Part B) specifies the data to collect at study intervention discontinuation and Follow-Up, and any additional evaluations that need to be completed.

If a participant's study intervention must be discontinued, this will not result in automatic withdrawal of the participant from the study and the participant should be assessed at the End-of-Treatment visit and Safety Follow-Up visit.

A participant's study intervention should be discontinued if:

- The Investigator believes that for safety reasons (eg, AE) it is in the best interest of the participant to discontinue study intervention.
 - The participant becomes pregnant.
 - The participant (or the participant's legally authorized representative) withdraws consent for administration of study intervention.
 - The participant's dose is held for more than 5 days per cycle, or if ≥ 6 consecutive planned doses of M3258 are missed for reasons other than toxicity unless, upon consultation with the Sponsor and the review of safety and efficacy, continuation is agreed upon.
 - The participant experiences disease progression.

Safety Stopping Rules for Study Intervention in Part B:

Unacceptable toxicity in the expansion cohort is defined as AEs that meet the DLT criteria regardless of when they occur during treatment (as defined in Section 6.6). The following stopping rules for unacceptable toxicity apply:

- ≥ 5 participants with observed DLT criteria out of 12 evaluable participants treated on the same dose.
- ≥ 7 participants with observed DLT criteria out of 18 evaluable participants treated on the same dose.
- ≥ 9 participants with observed DLT criteria out of 24 evaluable participants treated on the same dose.
- The chance is $>80\%$ that the true DLT rate is $\geq 30\%$ (based on Bayes model).

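### The SMC-discretion DLT item in Protocol 6.6 ends by admitting any Cycle 1 toxicity, which read literally empties the graded thresholds and overrides all 8 named exceptions

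*Protocol*

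**What the plan says.** Protocol 6.6 defines a DLT as a listed AE in the first treatment cycle that is "judged not to be related to the underlying disease or any previous or concomitant medication or concurrent condition". The assessment is made by the investigator and/or the sponsor, and "Any DLT must be confirmed by the SMC"; the confirmation requirement is repeated after the list.

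The list is graded. Nonhematologic AEs count from Grade 3, with six exceptions that begin with "Single laboratory values out of abnormal range that have no clinical correlate". Hematologic AEs count from Grade 4, plus certain named events, with two exceptions, the second being "Any Grade 4 neutropenia of < 7 days duration not associated with any clinical symptoms". Hy's law cases, deaths and neuropathy have their own items.

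A further item covers treatment-emergent AEs that the SMC finds clinically relevant. It closes with "at any time in Cycle 1 and any toxicity at any time in Cycle 1".

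Other provisions depend on the definition:
- Protocol 6.6: "Participants who develop a DLT will permanently discontinue treatment".
- Protocol Appendix 5: each event meeting the 6.6 criteria goes into the CRF within 24 hours.
- Protocol 7.1 (Part B): "Unacceptable toxicity in the expansion cohort is defined as AEs that meet the DLT criteria regardless of when they occur during treatment". Stopping boundaries are stated as numbers of participants with observed DLT criteria.
- SAP 15.1: DLTs by investigator flag and DLTs by SMC decision are tabulated separately. The Bayesian logistic regression model is updated with SMC decisions.

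**The concern.** DLT occurrence is a primary endpoint in both parts of the study. The condition that the SMC finds an event clinically relevant attaches grammatically to the treatment-emergent AE at the start of the item. The toxicity named at the end is a second noun phrase with no condition of its own. Someone applying the list as written could conclude that a Grade 1 event in Cycle 1, if not attributed to disease, other medication or a concurrent condition, meets the definition.

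What would be at stake is consistency between sites in what is flagged as a DLT, and whether a participant with no effective standard therapy is taken off treatment for an event that the rest of the list was written to tolerate.

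**Working it through.** **1. Count of exceptions (Protocol 6.6).**
- Nonhematologic: isolated laboratory values; Grade 3 diarrhea; nausea and vomiting; transient fatigue, local reactions, flu-like symptoms, fever and headache; skin toxicity; lipase or amylase elevation. That is 6.
- Hematologic: isolated Grade 4 lymphopenia; short asymptomatic Grade 4 neutropenia. That is 2.
- Total: 6 + 2 = 8.

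**2. The clause against the rest of the list.** The list is disjunctive: an event that meets any one item is a DLT, subject to attribution and confirmation.
- *Literal reading.* An excepted event, for example Grade 3 diarrhea that settles within 72 hours of starting management, is still a Cycle 1 toxicity. It therefore re-enters through the trailing clause. The same holds for each of the 8 exceptions, so 8 of 8 are overridden. The graded items are not negated, but they are absorbed: every event they capture is already captured, and the thresholds separate nothing.
- *Reading under SMC judgement.* A Cycle 1 toxicity that the SMC finds clinically relevant is already covered by the opening words of the item. The clause adds no event.

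So the clause is either in conflict with the list or redundant.

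**3. Where the written criteria act before or apart from SMC confirmation.**
- *CRF flag.* Recording is due within 24 hours. Under Protocol 9.4.4 the SMC cut-off normally comes when the last participant of the cohort completes the DLT period or discontinues. The flag therefore normally precedes the SMC decision and rests on the wording of 6.6.
- *Discontinuation.* Section 6.6 does not say whether stopping treatment waits for confirmation.
- *Part B boundaries.* The rules in 7.1 (5 of 12, 7 of 18, 9 of 24) count participants with observed criteria and do not restate confirmation. Meeting one pauses accrual for SMC review.

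**4. Whether the dose-toxicity model is affected.** Inputs are from Protocol Appendix 10: logit p(d) = α + exp(β)·log(d/90), with α ~ N(−0.708, 1.2²) and β ~ N(−0.389, 0.9²) independent. Four million prior draws give mean DLT probabilities of 14.7%, 18.8%, 23.5% and 27.5% at 10, 20, 35 and 50 mg, against 15%, 19%, 24% and 28% in Protocol 9.4.2. The plan's figures are reproduced to within 1 point.

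Suppose, purely as an illustration, that 3 participants at 10 mg have no Grade 3 event and one has a low-grade toxicity. Weight each draw by p^x(1 − p)^(3 − x), and compute the loss as 1·P(p ≤ 0.20) + 2·P(0.35 < p ≤ 0.60) + 3·P(p > 0.60).

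| DLTs counted | Posterior mean at 10 mg | Loss at 10 / 20 / 35 / 50 mg | Minimum-loss dose |
|---|---|---|---|
| 0 of 3 | 7.7% | 0.948 / 0.928 / 0.925 / 0.954 | 35 mg |
| 1 of 3 | 23.1% | 0.964 / 1.068 / 1.237 / 1.385 | 10 mg |

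One event would matter if it entered the model. Under SAP 15.1 it enters only if the SMC decides that it is a DLT, so the second row does not follow from the clause alone.

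**The case against.** The best defence is that the whole item belongs to the SMC. It opens with SMC judgement, the next item also turns on the SMC's opinion, and confirmation is required both before and after the list. The thresholds and exceptions themselves show that the literal reading was not intended. All of that stands, and it is why the effect is small. It does not rescue the clause, which on that reading is surplus.

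A second defence is that an exception qualifies only its own item, so the SMC could in any case call an excepted event a DLT. That is correct. But doing so takes a judgement of clinical relevance, which the trailing words do not require.

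The exposed steps are also partly covered. The SAP separates investigator and SMC DLTs, and the SMC analysis plan (SAP Appendix 18.1, Section 15.1) expects the two to differ and requires the investigator listing to be titled as such. Section 6.9.1 contemplates resuming at a lower dose after a DLT, so some doubt about discontinuation exists without this clause. Section 7.1 takes its criteria from 6.6, where confirmation is required.

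A reader might also infer that the clause contradicts the delay rule in 6.9.1, under which, if a delay in the next cycle of "more than two weeks is required because of incomplete recovery from toxicity, then this event should be considered a DLT". The documents do not support that. The rule adds one sufficient route to a DLT; it does not say that this is the only route, and it is not confined to Cycle 1. At most the literal clause makes it redundant for Cycle 1 toxicity.

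**Conclusion.** Wrong as written, minor severity. A primary endpoint definition contains an unlimited clause that is either in conflict with the list around it (8 of 8 exceptions overridden, thresholds without effect) or redundant.

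Two larger conclusions would go too far. One is that DLT counts in the model, and hence the MTD, are inflated. SMC confirmation and the SAP's use of SMC decisions stand in the way, and no misclassified participant is shown. The other is that the Part B boundaries measure the problem. They are fixed counts, and the documents give no any-grade toxicity rate from which to say how often the clause would contribute to them.

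The practical exposure is therefore limited to inconsistent investigator flagging, uncertainty about when permanent discontinuation applies, and the Part B accrual pause. SAP Section 7 records that the study stopped before Part B began, so only the first two could have arisen in this trial. The conclusion assumes that the SMC applied its own judgement when confirming DLTs, as Section 6.6 requires.

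**What to change.** In Protocol 6.6, within "at any time in Cycle 1 and any toxicity at any time in Cycle 1", delete everything after the first mention of Cycle 1 and keep the rest of the item. The SMC still has discretion over any clinically relevant Cycle 1 event, including one exempted from the graded items, and the separate item on later cycles is untouched. The cost is one clause struck by amendment. Sample size, prior, loss function and stopping boundaries do not change.

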Severity of Peripheral Neuropathy Signs and Symptoms ^a	Modification of Dose and Regimen
Grade 1 (asymptomatic: loss of deep tendon reflexes or paresthesia) without pain or loss of function	No action
Grade 1 with pain or Grade 2 (moderate symptoms: limiting instrumental ADL ^b)	Reduce M3258 dose by one dose level (based on dose escalation part) or at least by 50% if no lower dose level is available
Grade 2 with pain or Grade 3 (severe symptoms: limiting self-care ADL ^c)	Withhold M3258 therapy until toxicity resolves to Baseline or Grade 1 without pain, then reinitiate with a reduced dose of M3258 by one dose level (based on dose escalation part) or at least by 50% if no lower dose level is available If recurrence to Grade 2 with pain or higher, permanently discontinue M3258.
Grade 4 (life-threatening consequences: urgent intervention indicated)	Permanently discontinue M3258.

ADL = Activities of daily living; DLT = Dose-limiting toxicity; NCI = National Cancer Institute.

a Grading based on NCI Common Terminology Criteria for Adverse Events (CTCAE) v5.0.

b Instrumental ADL: refers to preparing meals, shopping for groceries or clothes, using telephone, managing money etc.

c Self-care ADL: refers to bathing, dressing and undressing, feeding self, using the toilet, taking medications, and not bedridden.

Table 12 Dose Modifications and Temporary/Permanent Treatment Discontinuation for Hematologic Toxicity (outside of DLT Period)

Hematologic Toxicity	Dose Modification
Neutropenia Grade 3 (without complications)	No dose reduction, consider treatment with G-CSF
Grade 3 Neutropenia associated with fever ($\geq 38.5^{\circ}\text{C}$) or neutropenia Grade 4	Hold M3258 until recovery to Baseline OR \leq Grade 2. Upon recovery, restart M3258 at current dose and consider G-CSF support. If recurrence is seen, reduce M3258 by one dose level (based on dose escalation part) or at least by 50% if no lower dose level is available. If second occurrence, permanently discontinue dosing
Thrombocytopenia Grade 3 (without complications)	No dose reduction required
Platelet count $< 25,000 / \mu\text{L}$ (i.e., Grade 4) or Grade 3 thrombocytopenia with bleeding	Hold M3258 until recovery to Baseline Or \leq Grade 2. Upon recovery, restart at a dose which is one dose level lower (based on dose escalation part) or at least by 50% if no lower dose level is available.

DLT = Dose limiting toxicity; G-CSF = granulocyte-colony stimulating factor.

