If applicable, repeat laboratory tests in the local laboratory within 72 hours and then repeat tests twice a week until recovery to Grade 2 is observed. Thereafter, repeat laboratory tests as appropriate based on Investigator's clinical judgement.

For clinically evident Grade 4 toxicities occurring after DLT period, discontinuation of M3258 administration is advised. A decision on re-initiation of M3258 should only be considered after recovery of toxicity in question to \leq Grade 1 is observed within two weeks of discontinuation of M3258 treatment (if a laboratory parameter, recovery should be confirmed by a repeat test), and the dose of M3258 should be reduced by at least 1 dose level. When a dose reduction is required, no re-escalation of the dose will be allowed. If Grade 4 toxicity recurs upon resuming M3258, then administration of study treatment should immediately be discontinued. The decision to continue treatment should be discussed with the Medical Monitor and documented in the study records. In case of the occurrence of overlapping toxicities of M3258 and dexamethasone, the dose reduction of M3258 will occur first (see [Table 11](#), [Table 12](#), and [Table 13](#)). Dexamethasone dose should be reduced based on local product label or institutional guidelines only for toxicities which are deemed related to dexamethasone (for related toxicities and guidance on dose reduction, see [Table 14A](#) and [Table 14B](#)).

In the event of new or worsening pulmonary symptoms, a prompt diagnostic evaluation and involvement of a pulmonologist should be considered. Participants will be treated according to institutional standards. Since low-grade pulmonary toxicities (Grade 1-2), such as dyspnea and cough, manifest as symptoms of diverse underlying etiologies, the study investigators should bear high suspicion for study treatment-induced pulmonary injury. The study investigator will also be required to discuss any grade pulmonary toxicity with the Sponsor medical representative. Re-initiation of M3258 must be discussed with the Sponsor medical representative. The benefit/risk balance should be considered prior to continuing M3258 therapy.

The adverse events suggestive of lung toxicity with Grade ≥ 3 irrespective of attributability will be reported as SAEs throughout the study.

Grade 4 toxicity should always be reported to the Sponsor as a SAE in expedited manner, within 24 hours of awareness.

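### For clinically evident, M3258-related Grade 4 neutropenia after the DLT period, Table 12 and Section 6.9.1 set conflicting defaults on recovery, restart dose and recurrence, and no text says which governs

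*Protocol*

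**What the plan says.** Section 6.6 of the Protocol introduces Table 12 as the rule for M3258-related hematologic toxicity outside the DLT period. One row covers any Grade 4 neutropenia. M3258 is held until Baseline or Grade 2 or lower, and then: "Upon recovery, restart M3258 at current dose and consider G-CSF support". Next comes "If recurrence is seen, reduce M3258 by one dose level (based on dose escalation part", with a cut of at least 50% where no lower level exists, and finally "If second occurrence, permanently discontinue dosing".

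Section 6.9.1 has a subsection on Grade 3 or 4 toxicities whose subheading names both hematological and nonhematological events. It states: "For clinically evident Grade 4 toxicities occurring after DLT period, discontinuation of M3258 administration is advised". Re-initiation may be considered only once recovery to at most "Grade 1 is observed within two weeks of discontinuation of M3258 treatment". On restart, "the dose of M3258 should be reduced by at least 1 dose level". Finally: "If Grade 4 toxicity recurs upon resuming M3258, then administration of study treatment should immediately be discontinued".

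The Grade 4 paragraph mentions Table 12 only in setting the order of reductions: "In case of the occurrence of overlapping toxicities of M3258 and dexamethasone, the dose reduction of M3258 will occur first", followed by a reference to Tables 11 to 13. Sections 6.6 and 6.9.1 each bar dose reduction in the first cohort.

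**The concern.** A participant with clinically evident, M3258-related Grade 4 neutropenia in Cycle 2 or later falls under both texts. Table 12 makes no exception for clinically evident cases. The 6.9.1 subheading expressly takes in hematological toxicity, and its paragraph even says how recovery of a laboratory parameter is to be confirmed.

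These are re-exposure rules after a Grade 4 event in a first-in-human trial. Two sites reading the same protocol could restart at full dose or at a reduced dose. They could also answer the first recurrence with a reduction or with a permanent stop.

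**Working it through.** No figure in the plan needs to be reproduced. The check sets the two texts side by side for one event: clinically evident, M3258-related Grade 4 neutropenia after the DLT period.

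| Decision | Table 12 (Section 6.6) | Grade 4 paragraph (Section 6.9.1) | Same? |
|---|---|---|---|
| Recovery before restart | Baseline, or Grade 2 or lower | Grade 1 or lower | No |
| Restart dose | Current dose | At least one level lower | No |
| First recurrence | Reduce and continue | Discontinue | No |

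**Count.** Neutropenia: 3 of 3 decisions differ. For Grade 4 thrombocytopenia, both texts require a lower restart dose, and Table 12 is silent on recurrence, so 6.9.1 fills a gap without contradicting anything. Only the recovery grade differs: 1 of 3.

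**What is not a difference.** The two-week limit in 6.9.1 adds nothing. Section 6.6 already requires permanent discontinuation if dosing is withheld for more than two weeks for any reason, which binds Table 12 as well.

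**Direction of the conflict.** Recovery to Grade 1 also satisfies Grade 2 or lower. Section 6.6 permits a safety reduction at any time outside the first cohort, and Section 7.1 lets the Investigator stop treatment for safety. A site that takes the 6.9.1 path therefore stays within Section 6.6. The reverse fails: a full-dose restart under Table 12 departs from 6.9.1.

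**First cohort (10 mg QD, Section 4.1).** Reduction is barred. The reduced restart that 6.9.1 sets as a condition is unavailable, so the participant stays off drug. Table 12 allows a restart at 10 mg daily, but its own reduction at recurrence cannot be carried out.

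**Weekly restart dose** for the three groups named in SAP Section 14.2, Table 12 against 6.9.1:

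- 10 mg QD (taken as the first cohort): 7 × 10 = 70 mg against no permitted dose.
- 10 mg twice weekly: 2 × 10 = 20 mg against at most 2 × 5 = 10 mg. This assumes that the 50% fallback of Section 6.6 also applies under 6.9.1, which does not state one.
- 20 mg twice weekly: 2 × 20 = 40 mg against at most 2 × 10 = 20 mg.

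**Recovery grade, an example.** Inclusion criterion 5c admits participants with an ANC of 1,000/mm³ or more. SAP Section 15.4, in its rule for laboratories without an absolute-count range, puts the lower edge of Grade 1 at 1,500/mm³. Using that edge, take a participant back at a Baseline ANC of 1,000 to 1,499/mm³ in mid-cycle. Table 12 allows the restart; the Grade 4 paragraph, which has no Baseline alternative, does not. The cycle-start criteria in 6.9.1 itself accept 1,000/mm³. G-CSF is barred only in the DLT period, so this does not show that 1,500/mm³ would be missed within two weeks.

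**The case against.** The best case for the plan is that a reader can tell that Table 12 is meant. Section 6.6 assigns M3258-related hematologic toxicity to it, Table 15 sends complicated myelosuppression above Grade 3 to it, and the title of 6.9.1 speaks of other toxicities. The current amendment summary also records a recent adjustment of this very row. All of that is true and determines the direction of the fix. None of it disapplies the Grade 4 paragraph, whose own subheading names hematological events.

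Second, 6.9.1 is worded as advice, and the sponsor is always involved. Grade 4 toxicity goes to the sponsor as an SAE within 24 hours, dose changes and deferrals are discussed with the Sponsor Medical Responsible, and continuation is discussed with the Medical Monitor and documented. This makes silent divergence between sites unlikely, and it limits the impact. It is case-by-case consultation, not a rule of precedence.

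Third, the SMC may classify a related later-cycle event as a DLT, and participants with a DLT discontinue permanently. That would take some cases out of both restart rules, but only those so classified.

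A reader might go further and infer that the two texts cannot be reconciled at all, or that the first cohort has no workable instruction. The documents do not support either reading. The stricter path is open under Sections 6.6 and 7.1. In the first cohort 6.9.1 yields a strict but usable default: discontinuation is advised, the condition for restart cannot be met, and the participant stays off drug.

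**Conclusion.** The point holds as a conflict of defaults. Table 12 directs a full-dose restart that 6.9.1 rules out, and the texts also part on recovery grade and first recurrence: 3 of 3 decisions for neutropenia and 1 of 3 for thrombocytopenia. The first cohort adds a gap, since Table 12's reduction on recurrence is not available there.

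The conclusion is confined to clinically evident, M3258-related events after the DLT period. The protocol does not define clinically evident, so asymptomatic laboratory Grade 4 neutropenia is left out. The documents give no event frequency, so the number of participants affected cannot be stated.

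It would be tempting to infer that DLT estimates or dose-escalation decisions are affected. Nothing in the documents shows that: the rules apply outside the DLT period, the analyses are descriptive, and no estimate or DLT rule is shown to change. SAP Section 7 adds that the trial stopped before Part B. The point should still be fixed, because it governs re-exposure after a Grade 4 event and the correction is small.

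**What to change.** Add to the Grade 4 paragraph of 6.9.1 that M3258-related neutropenia and thrombocytopenia follow Table 12 for recovery grade, restart dose and recurrence. Two further changes belong in the same amendment:

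- In Table 12's thrombocytopenia row, state that recurrence of Grade 4 after resuming leads to permanent discontinuation. Without this, sending thrombocytopenia to Table 12 would remove the stop rule that 6.9.1 now supplies.
- State that where a reduction is called for in a first-cohort participant, M3258 is permanently discontinued.

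If the sponsor intends the stricter rule for clinically evident Grade 4 neutropenia, the Table 12 row should be amended to match 6.9.1 instead. That is a clinical choice, and either direction removes the conflict. Numbering the occurrences in the neutropenia row (first: hold and restart; second: reduce; third: discontinue, if that is the intent) is an optional wording improvement.

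The cost is a few sentences and the IRB/IEC approval that Appendix 2 requires for an amendment, with no added procedures or participants. As the trial has stopped, the correction matters mainly before this text is reused.
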